## 13.0

# Data and Safety Monitoring Plan

### 13.2 \* DATA AND SAFETY MONITORING PLAN: (REQUIRED)

**All greater than minimal risk studies are required to provide a plan. Lack of an adequate plan is one of the most common reasons why IRB approval is delayed.**

#### **Instructions:**

Describe the plan for monitoring data quality and participant safety. Key areas that should be included in the plan are:

- An explanation of the plan to monitor data collection, study progress, and safety
- A description of who will perform the monitoring and at what frequency (e.g., the PI only, a contract research organization, a Data and Safety Monitoring Board or Data Monitoring Committee, etc.)
- The type of data and events that will be reviewed (e.g., adverse events, breaches of confidentiality, unanticipated problems involving risk to participants or others, unblinded efficacy data, etc.)
- Procedures and timeline for communicating monitoring results to the UCSF IRB, the study sponsor, and other appropriate entities
- Assurance that the research team will adhere to the **UCSF IRB reporting requirements**

As appropriate:

- A plan for conducting and reporting interim analysis
- Clearly defined stopping rules
- Clearly defined rules for withdrawing participants from study interventions

#### **DATA AND SAFETY MONITORING PLAN**

Procedures for implementing a Data Safety and Monitoring Plan (DSMP) at the University of California San Francisco have been developed on a campus-wide basis in conjunction with the Institutional Review Board (called the Committee on Human Research at UCSF), the Office of the Vice-Chancellor for Research, and the Office of Clinical Research in the School of Medicine. The Data and Safety Monitoring Plan for the proposed project incorporates the policies on human subject data and safety monitoring specified by the UCSF Committee on Human Research (i.e. UCSF IRB).

#### **1. Risk Assessment – Minimal Risk**

This study represents a minimal risk non-therapeutic behavioral intervention. It encompasses a randomized controlled trial among 640 participants with the intervention tested being an online workshop (*Building Better Caregivers*) that focuses on improving participants' self-care practices and skills for dementia caregiving. Data collection is performed through use of online surveys and phone-based interviews. The Research Assistant (RA) will be trained by [name], the PI, who is a

self-management expert and practicing primary care physician, with expertise in chronic disease management and caregiver and self-management research. In the course of the study, we will have several safeguards in place to quickly identify and respond to participants who we feel might require professional mental health assessment and services or other forms of medical assessment or care. To decrease the likelihood of an adverse event during the study, the RA will receive intensive training from the PI, [name], and the Project Coordinator on procedures for reporting adverse events, how to recognize symptoms of clinical depression or anxiety, and the need to call the PI when she feels that a participant requires additional services from a mental health or health care professional.

For participants who are randomized to receive the *Building Better Caregivers* workshop initially or who choose to attend it later after they have finished participation in the control group, during the workshop they will receive training on healthy self-care practices and perform self-efficacy building activities, including those that may improve their mental and physical well-being. For example, the workshop contains modules on managing stress and difficult emotions including symptoms of anxiety, depression, anger, and fatigue. Participants may respond to these modules by experiencing and/or disclosing their experiences of stress and difficult emotions. In light of this, the *Building Better Caregivers* workshop itself is staffed by peer facilitators who receive rigorous training on the management and triage of participants experiencing difficult emotions, which includes when and how to activate built-in safety protocols—such as contact of the overseeing health professional if a participant indicates they are at any risk for self-harm. Facilitators keep track of all participants by electronically checking in with them at least once weekly during the 6-week workshop. They also observe all online interactions and postings daily throughout the workshop. The activities of the facilitators are themselves reviewed by "Master Trainers" who monitor the fidelity, quality, and safety of workshop delivery. Workshop participants also receive training on how to contact their workshop facilitators. The workshop safety protocols already in place have been used successfully in the existing provision of a version of the workshop to over 3,000 caregivers of veterans by the Veterans Affairs Health Care System (see Preliminary Studies section of the Research Strategy for details on the workshop for veteran caregivers), with activations of the safety protocol being extremely rare (3 times in 24 months) with successful resolution with participant safety being assured in all cases. The *Building Better Caregivers* workshop safety protocol for the purpose of this study will include the addition of the study PI being informed of all safety protocol activations.

In all cases when the PI is alerted to a potential safety issue, whether by the study RA, Project Coordinator, or the *Building Better Caregivers* workshop safety protocol, The PI will proceed to address these as potential adverse events. Adverse events will be graded according to their significance for severe consequences, such as injury or death. If the event is determined to be an AE that is moderate or higher in degree, [name] will then contact the participant directly to assess the situation, make appropriate referrals, and follow-up with the participant and RA. The participant will have given previous consent for the PI to contact him/her directly when such an assessment is indicated in the opinion of the RA or Project Coordinator or by activation of the BBC workshop safety protocol. Furthermore, study participants will have the full contact information for the study team, including email and telephone contact details, so that problems will be identified in a timely manner, and should be alleviated by the support and coping skills before the problem becomes more serious or chronic. Finally, at the time of enrollment in the study, the study team will provide participants with a list of health resources available to them, which will include mental health services and hotline numbers.

## **2. Description of Adverse Event Grading and Anticipated Adverse Events**

An adverse event (AE) is here defined as any unfavorable and unintended sign, symptom, injury or disease temporarily associated with an intervention or procedure, regardless of whether it is considered related to an intervention or procedure that occurs during the course of the study. AEs will be scored as follows:

0. = No adverse event or within normal limits
1. = Mild AE – not requiring treatment/follow-up
2. = Moderate AE – resolved with follow-up
3. = Severe AE – resulted in inability to carry on normal activities, requiring hospitalization
4. = Life-threatening or disabling AE – results in an immediate risk of death and/or results in persistent or significant disability
5. = Fatal AE

Adverse events categorized as severe, life-threatening/disabling, or fatal are by definition serious adverse events. Examples of the types of adverse events we might encounter in the proposed study are as follows:

1. Mild AE (ones that do not require treatment/follow-up): reports of depressive symptoms, anxiety, and stress that do not interfere with normal activities; fatigue from answering study questions (via online survey—and for a sub-set, phone-based interviews); frustration when learning to use the online workshop site; anxiety about the ability to complete activities for the workshop; and worry about loss of confidentiality/privacy.
2. Moderate AE (ones that resolve with treatment/follow-up): experiences of transient episodes of depressive symptoms or anxiety attacks that modestly affect daily activities and resolve with lifestyle, stress management, or usual care approaches.
3. Severe AE (ones that result in inability to carry on normal activities, those requiring hospitalization): patient is so anxious or depressed that they enter a hospital or day-treatment facility.
4. Life-threatening or disabling AD (ones involving immediate risk of death or persistent disability): participant threatening or attempting self-harm or harm to others. These events are extremely rare and occur more often in participants with a history of depression.

Given that the proposed intervention is behavioral and educational in nature, we anticipate that mild AEs will comprise the overwhelming majority of reported AEs. The PI, in consultation with the research team, is responsible for evaluating each AE and for notifying the project's Data and Safety Monitoring Board and the UCSF Committee on Human Research of the occurrence of adverse events.

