attention control group. Caregivers will be recruited through 19 community organizations (serving rural communities in 17 states). Primary outcomes will be caregiver stress and depression symptoms. We hypothesize that stress scores and depression symptoms will be significantly improved at 12 months in the intervention group versus control group. We will also identify key strengths (facilitators) and weaknesses (barriers) of workshop implementation. We will use the RE-AIM implementation framework and a mixed methods approach to identify implementation characteristics pertinent to both caregivers and rural community organizations.

If the *Building Better Caregivers* workshop is proven to be effective, this research has the potential to open new research horizons, particularly on how to reach and effectively support isolated dementia caregivers in rural areas with an intervention that is scalable, even in low-resourced settings. If the workshop can achieve its goals with rural dementia caregivers, some of those most isolated, it would also be expected to be scalable in other low-resourced settings (e.g., in urban or suburban environments).

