b. **Attention control group.** Participants will receive written materials on dementia and caregiver resources and two brief phone calls of 15-30 minutes apiece by research staff. Caregivers in the attention control group will be offered the online workshop after the 12 month trial is completed if they so desire. The written materials and phone call guides are still under development and will be submitted to the IRB for review as a modification request.

**For control group fidelity purposes.** Phone calls will be recorded. [name] and the research coordinator will evaluate recordings using a fidelity assessment instrument. Staff who stray from the phone call protocol will receive immediate remedial training. If an RA strays from the protocol again, he/she will be removed from making phone calls. At the outset of the trial, fidelity assessment will occur approximately every 4-5 calls to assure fidelity patterns are quickly established and reinforced. Subsequent checks will occur every 10-12 calls.

5. **Assessments:** Data will be collected at baseline, 1.5 months (post intervention), 6 months, and 12 months. Data will be collected through online surveys completed by caregivers and conducted at baseline, post-intervention (1.5 months), and 6, and 12 months using the secure REDCap application. Assessments are expected to be 20 minutes each. Participants will be given the option to complete surveys by mail or phone interview.

a. **Baseline** questions will ask about caregiver and PWD demographic information (e.g., age, gender, race/ethnicity, education); caregiving relationship to PWD (e.g., spouse, child), and resources participants are accessing (e.g., paid in-home care). Baseline questions also will identify caregiver and partner chronic conditions (e.g., using the Charlson comorbidity index), partner need for assistance with ADLs and IADLs, and dementia characteristics (e.g., diagnosis, length of diagnosis, degree of impairment, presence of behavioral symptoms). Caregiver (CG) stress level (Stress visual numeric scale), CG depression symptoms (PHQ-8 score), Self-efficacy (Revised Scale for Caregiver Self-efficacy), Burden (Zarit Burden Inventory), Strain (Caregiver Strain Index), Global health score, and Healthcare utilization items.

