#### **4. Plans for Assuring Compliance with Requirements Regarding the Reporting of Adverse Events**

The PI is responsible for reporting adverse events to the research team, to the DSMB, and to the CHR. Mild and moderate adverse events will be reported within 10 working days of the occurrence or knowledge of the occurrence. Severe, life-threatening or fatal adverse events will be reported immediately to the PI, who will notify the CHR within 48 hours. This means that research assistants will be trained to recognize, respond to, and record adverse events when they occur or immediately after they occur to insure the safety of the human subjects; and to report adverse events to the PI in a timely manner to insure compliance with institutional policies on human subject protection. This also means that research assistants engaged in data collection will be able to contact the PI as soon as an adverse event occurs. Specifically, the PI will report the following information in writing to the DSMB and UCSF CHR: 1) all severe adverse events associated with the study procedures, and/or 2) any incidents or problems involving the conduct of the study or patient participation, including problems with the recruitment and/or consent processes and/or education of participants about managing stress and coping with depression symptoms. The PI also will provide a written report of adverse events of moderate or greater severity during the course of the study to the CHR on an annual basis.

Severe adverse events are very rare in persons engaging in self-management and educational activities, although it is possible that a person with previously unidentified depression, anxiety disorder, or other mental illness may experience an aggravation during times of stress. We will stop the study based on instructions from the DSMB or CHR, which will be notified immediately if a participant in this study experiences a severe adverse event while enrolled in the study.

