#### **7. Stopping Guidelines**

The study will terminate if subjects experience a significantly large number of adverse events.

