## **Meeting Format**

The DSMB meetings will consist of an open and a closed session, both closed to the public because discussions may address confidential participant data. The study PI and key staff members, DSMB members and NIA Project Scientist attend the open sessions. Discussions at these sessions focus on the review of the aggregate data, conduct and progress of the study, including participant accrual, protocol compliance, and problems encountered. Data by blinded treatment group and unblinded data are not presented in the open session. The primary objective of the closed sessions is to review data by blinded study group and, if requested by the DSMB, unblinded data. The closed sessions are attended by the DSMB members, the NIA Program Officer and an unblinded study statistician. The NIA Program Officer attends the closed and open sessions as an observer, not as a DSMB member to answer any policy or administrative questions the DSMB members may have. If necessary, an executive session may be requested by the DSMB and will be attended only by voting DSMB members. The NIA Program Officer is not permitted to attend the executive sessions.

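### Adverse events overlap the primary outcomes and are not collected the same way in both arms, so the by-group safety comparison is open to detection bias

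*Combined protocol and SAP*

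**What the plan says.** All references are to the combined protocol and SAP unless stated.

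- **Definition (13.2, item 2).** An adverse event is counted "regardless of whether it is considered related to an intervention or procedure that occurs during the course of the study". The first mild example is "reports of depressive symptoms, anxiety, and stress that do not interfere with normal activities". Two further mild examples, frustration with the workshop site and anxiety about workshop activities, can arise only in the workshop arm during the trial. Mild events are expected to dominate.
- **Outcomes (4.1).** "Primary outcomes will be caregiver stress and depression symptoms".
- **Workshop arm (13.2, item 1; 8.10).** Facilitators check in at least weekly for six weeks. "They also observe all online interactions and postings daily throughout the workshop". Fidelity monitors, who may be research staff, review recordings weekly.
- **Control arm (8.10, item 4b).** Written materials and "two brief phone calls of 15-30 minutes apiece by research staff".
- **Both arms (8.10, item 5; 13.2, item 1).** The same PHQ-8, stress, burden, strain, global health and healthcare-utilization items at every survey, and contact details for the study team. No adverse-event question is listed.
- **Reporting (13.2, item 4).** "Mild and moderate adverse events will be reported within 10 working days of the occurrence or knowledge of the occurrence". Research assistants are trained to recognize and record adverse events.
- **Use (13.2, DSMB Charter).** "The primary objective of the closed sessions is to review data by blinded study group", and the closed report carries safety data.
- **Stopping (13.2, item 7).** "The study will terminate if subjects experience a significantly large number of adverse events".
- **Allocation.** The application plans 320 per arm. The power memo (the Protocol document) selects a ratio of 1:1, 2:1 or 3:1 according to accrual in each two-week period.

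**The concern.** Two features combine. First, the commonest expected class of adverse event includes the symptoms that the trial measures as efficacy, in caregivers whom Section 10.7 selects for higher burden. Nothing says whether a symptom present before randomization counts, or how a symptom reported during follow-up is separated from the outcome itself.

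Second, whether such a symptom is recorded depends on someone noticing it, and the opportunity to notice differs by arm. The workshop includes a discussion board on difficult emotions, and the plan expects participants to disclose stress there. Controls have no comparable setting.

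A between-arm difference in adverse events could then reflect how closely each arm was watched. The DSMB reviews safety data by group and recommends whether the trial continues, so it needs a comparison that can be read as a treatment effect.

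**Working it through.** The plan states no expected event rate, detection probability or threshold, so there is no figure of its own to reproduce. The check sets the routes side by side and then shows how sensitive the comparison is.

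**1. Routes by which an event can become known**

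| Route | Workshop | Control |
|---|---|---|
| Facilitator check-in, at least weekly for 6 weeks | yes | no |
| Posts read daily for 6 weeks | yes | no |
| Recordings reviewed for fidelity | weekly | a sample of calls (every 4-5, later every 10-12) |
| Staff calls | none planned | 2 |
| Surveys at 1.5, 6 and 12 months | yes, no adverse-event item listed | same |
| Self-report to the study team | yes | same |

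**2. Planned contact (Section 11.13).** Workshop: 120 × 6 = 720 minutes. Control: 2 × 15 = 30 to 2 × 30 = 60 minutes. Ratio: 720/60 = 12 to 720/30 = 24. This measures opportunity, not detection.

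**3. The facilitators' stated alert route alone.** Section 13.2, item 1 reports 3 safety-protocol activations in 24 months, among more than 3,000 caregivers of veterans. Assuming that those figures share a denominator, the rate is 3/3,000 = 0.001. Expected activations are 0.001 × 320 = 0.32, or 0.001 × 480 = 0.48 if all allocation were 3:1. This route adds less than one event, so any material bias must come from milder symptoms recorded by other means.

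**4. Illustration if mild symptoms are recorded.** All inputs here are assumptions. The true risk p is equal in both arms, detection is s_w in the workshop and s_c in control, and n = 320 per arm. Observed risks are p·s_w and p·s_c. The chance that a two-sided 5% test falsely shows the workshop as worse is about Φ((Δ − 1.96·SE₀)/SE₁), where Δ is the difference in observed risks and SE₀ and SE₁ are the pooled and unpooled standard errors.

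For p = 0.3 and detection 0.3 against 0.2: observed risks 0.09 and 0.06, Δ = 0.03, SE₀ = √(2 × 0.075 × 0.925/320) = 0.0208, SE₁ = √((0.09 × 0.91 + 0.06 × 0.94)/320) = 0.0208. The chance is Φ(−0.52) = 0.30.

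| p | s_w / s_c | Expected events | Chance of false flag |
|---|---|---|---|
| 0.1 | 0.3 / 0.2 | 9.6 vs 6.4 | 0.125 |
| 0.1 | 0.4 / 0.2 | 12.8 vs 6.4 | 0.316 |
| 0.1 | 0.6 / 0.2 | 19.2 vs 6.4 | 0.734 |
| 0.3 | 0.3 / 0.2 | 28.8 vs 19.2 | 0.302 |
| 0.3 | 0.4 / 0.2 | 38.4 vs 19.2 | 0.757 |
| 0.3 | 0.6 / 0.2 | 57.6 vs 19.2 | 0.997 |
| any | equal | equal | 0.025 |

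If the staff calls detect more than the workshop does (0.2 against 0.3, p = 0.3), the picture reverses: 19.2 vs 28.8 events, with a 0.302 chance of falsely flagging control.

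**5. Allocation.** With equal detection of 0.3 and p = 0.3, the observed risk is 0.09 in each arm. Expected counts from 640 caregivers are 28.8 vs 28.8 at 1:1, 38.4 vs 19.2 at 2:1, and 43.2 vs 14.4 at 3:1. The last two are bounds, because the ratio varies over the trial. Raw counts differ with no harm and no detection bias; proportions do not.

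**The case against.** The strongest reply is that daily observation is tied to adverse-event reporting only through the safety protocol. Section 12.3 triggers that protocol on a perceived imminent danger, and it was activated very seldom. No section tells facilitators to log mild symptoms. This stands as a limit on size, but it is not complete: Section 13.2, item 1 describes a wider trigger (any risk of self-harm), and research staff may review workshop recordings weekly while research assistants are trained to record events. That second route is an inference from two sections, not a stated procedure.

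It can also be said that staff trained to recognize depression and anxiety speak directly to controls, whereas workshop facilitators are peers. That stands too, and it is why the direction is likely rather than certain.

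Three stronger readings are tempting, and the documents do not support them.

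- A reader might infer that deterioration in controls goes largely unseen. Both arms complete the same PHQ-8, stress and healthcare-utilization items, and the closed report includes outcomes.
- A reader might infer that every survey yields an adverse event, up to 640 × 4 = 2,560. No section makes a survey score an adverse event, the quoted text is an example, and the definition also asks that a symptom be unintended and linked in time to an intervention or procedure.
- A reader might infer that the stopping guideline is biased against the workshop. It pools participants and compares no arms; it is undefined, which is a different weakness.

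The Manual of Procedures, the attached safety protocol and the control call guides are not in these documents and could hold a common query. If so, the plan should cite it.

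**Conclusion.** The concern holds in this form: adverse-event collection is not standardized across arms, the definition overlaps the primary outcomes without reference to baseline, and the by-group data reviewed by the DSMB are therefore open to detection bias, probably but not certainly against the workshop. Raw counts would also differ under 2:1 or 3:1 allocation.

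The size cannot be derived from the documents. The illustration shows only that modest differences in detection could matter if mild symptoms are recorded; if facilitators' alerts were the only differing route, the effect would be under one event. The primary efficacy comparison, which rests on identical surveys, is not affected. The item 7 guideline needs clarifying, but the documents do not show it to favour either arm.

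**What to change.** 1. Add one identical adverse-event question to the 1.5-, 6- and 12-month surveys in both arms.
2. Make it the main source for the between-arm comparison, reported as a proportion of each arm, with the numbers randomized and answering shown.
3. List events found through facilitators, recordings or calls separately by source. Serious events from any source should always be shown to the DSMB.
4. For the between-arm tabulation, count depressive and stress symptoms only when new or worse than the caregiver's own baseline. Keep PHQ-8 and stress scores as efficacy data.
5. The sponsor and DSMB should state what Section 13.2, item 7 counts. No threshold or rule is proposed here.

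The alert and response pathways for individual participants stay unchanged.

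The cost is one survey item, a wording change in 13.2 and a source column in the DSMB tables. The downsides are slightly longer surveys, longer recall for mild events and missing answers from non-responders. Participants know their assignment, so the question equalizes the opportunity to report but cannot guarantee equal reporting.
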